13. OTHER ANALYSES

There is no other analysis planned for this study.

14. INTERIM ANALYSIS

There is no interim analysis in this study.

15. DATA MONITORING/REVIEW COMMITTEE

There is no data monitoring committee for this study.

16. COMPUTER METHODS

Statistical analyses will be performed using Version 9.2 (or higher) of SAS[®] on a suitably qualified environment.

17. CHANGES TO ANALYSES SPECIFIED IN PROTOCOL

Since a decision has been made to early terminate the trial, an abbreviated Clinical Study Report (CSR) will be generated, which will contain a full report of information related to safety and abbreviated summary of efficacy evaluation. The majority of the efficacy analyses outlined in section 9.8, efficacy analysis section of the protocol will not be conducted. No hypothesis testing will be performed on any of the efficacy endpoint. Only descriptive statistics will be generated for clinical resolution status, ≥ 2 point reduction from baseline on GCS and adenoviral eradication status as outlined in section 10.2 of this SAP.

18. DATA HANDLING CONVENTIONS

18.1 General Data Reporting Conventions

Continuous variables will be summarized using the following descriptive statistics: number of subjects (n), mean, median, SD, minimum, maximum unless otherwise specified. Categorical and count variables will be summarized by the number of subjects (n), frequency and the percent of subjects in each category unless otherwise specified. Percentages will be presented with one decimal point.

See TFLs4Shire for rules on the number of decimal places to present data and p-values.

18.2 Study Visits and Windows

CRF visits will be used in all summary tables and listings.

Study day will be calculated as follows:

- If the assessment date is on or after the date of first instillation:

$$\text{Study day} = \text{assessment date} - \text{first dosing date} + 1$$

- If the assessment date is before the date of first instillation:

$$\text{Study day} = \text{assessment date} - \text{first dosing date}$$

18.3 Derived Efficacy Endpoints

Clinical resolution is defined as absence of bulbar conjunctival injection and watery conjunctival discharge. Bulbar Conjunctival Injection will be assessed based on a 0-4 scale which uses pictures from the Validated Bulbar Redness (VBR) Scale. Watery Conjunctival Discharge will be assessed based on a 0-3 scale. For both bulbar conjunctival injection and watery conjunctival discharge, 0 score indicates normal or none and a higher score indicates a higher severity of the clinical sign. A 0 sum of bulbar conjunctival injection score and watery conjunctival discharge score represents reaching clinical resolution. Any non 0 sum means not reaching clinical resolution. If either individual score is missing, clinical resolution status will be set to missing.

Adenoviral eradication is defined as negative CC-IFA (indeterminate CC-IFA result is considered negative CC-IFA). Positive CC-IFA is considered not reaching adenoviral eradication. If an eye has missing CC-IFA result at baseline, the eye will be assumed to be CC-IFA negative at baseline for determination of the study eye.

Global clinical score is defined as the sum of bulbar conjunctival injection score and watery conjunctival discharge score. If either individual score is missing, global clinical score will be set to missing.

Modified clinical resolution is defined as a global clinical score of 0 or 1. All other scores are considered not reaching modified clinical resolution. If either individual score is missing, modified clinical resolution status will be set to missing.

Expanded clinical resolution is defined as a global clinical score of 0, 1, or 2 with neither bulbar conjunctival injection score nor watery conjunctival discharge score having a score of 2. Otherwise, the subject is considered not reaching expanded clinical resolution. If either individual score is missing, expanded clinical resolution status will be set to missing.

Time to clinical resolution will be derived based upon assessments at Visits 2 (Day 3), 3 (Day 6), 4 (Day 8), and 5 (Day 12) in the study eye. Time to clinical resolution will equal to the study day corresponding to the visit when the subject first reaches clinical resolution in the study eye.

Cross over infection status will be assessed by CC-IFA results as follows:

Scenario		Cross-over Infection Status at Post Baseline Visit
Both eyes CC-IFA positive at baseline		Not applicable
Only one eye CC-IFA positive at baseline	The other eye CC-IFA positive at post baseline visit	Yes
	The other eye CC-IFA negative at post baseline visit	No
Both eyes CC-IFA negative at baseline		Not applicable

Ocular discomfort total score (in the version for adult and older children) is defined as the sum of eye pain score, the feeling that something was in your eye score and itching score. If any individual score is missing, then ocular discomfort total score will be set to missing.

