1. INTRODUCTION

This statistical analysis plan (SAP) provides a technical and detailed elaboration of the statistical analyses of efficacy and safety data as described in the final study protocol amendment 4.0 dated April 5, 2019. Specifications for tables, figures, and listings are contained in a separate document.

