4.3 Intent to Treat (ITT) Population

The ITT Population will include all randomized subjects.

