No hypothesis testing will be conducted for the efficacy endpoints. Clinical resolution status, ≥ 2 point reduction from baseline on GCS and adenoviral eradication status efficacy endpoints will be summarized by treatment group using descriptive statistics at each assessment visit in the mITT Population. Clinical resolution status will also be summarized by treatment group using descriptive statistics at each assessment visit in the ITT Population. These binary endpoints will be summarized by number of subjects (n), frequency, proportion and two-sided 95% CI (exact CI for binominal proportion). Other secondary endpoints will not be summarized by treatment group.

No hypothesis testing will be conducted for any efficacy endpoints.

All efficacy endpoints will be listed in ITT with a flag indicating whether the subject is in mITT population.

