Appendix 20.1 shows example SAS code for generating descriptive statistics:

10.3 Exploratory Efficacy Endpoints and Analyses

11. SAFETY ANALYSES

The safety analysis will be performed using the Safety Population. Safety variables include adverse events (AEs, including local tolerability), slit lamp biomicroscopy, non-dilated/dilated fundus exam, red reflex exam, best corrected visual acuity (BCVA), and urine pregnancy testing (for females of childbearing potential) variables. Safety data collected at baseline (Visit 1) will be used as the baseline value for safety analysis. All safety analyses will be conducted according to the treatment the subject actually received.

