20. APPENDIX

20.1 Example SAS Code for Generating Descriptive Statistics

```
*For binary endpoint;  
proc freq data = testData;  
tables binary_endpoint / binomial (exact level='Yes') alpha=0.05;  
by visit treatment;  
run;
```

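### As written, SAP 10.2 and 20.1 give observed-case clinical resolution rates even in the ITT table, with no stated denominator; a one-sign missing rule in 18.3 adds a small inconsistency (minor)

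*SAP*

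**What the plan says.** **Reporting.** For clinical resolution, the 2-point GCS reduction and adenoviral eradication, SAP 10.2 says: "These binary endpoints will be summarized by number of subjects (n), frequency, proportion and two-sided 95% CI". The main summary is in mITT, and for resolution a second one follows: "Clinical resolution status will also be summarized by treatment group using descriptive statistics at each assessment visit in the ITT Population". SAP 4.3 defines that population: "The ITT Population will include all randomized subjects". The corresponding tables in SAP 21 are 14.2.1.1 (mITT) and 14.2.1.4 (ITT).

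**Code.** The line closing 10.2 reads: "Appendix 20.1 shows example SAS code for generating descriptive statistics". The operative statement in 20.1 is "tables binary_endpoint / binomial (exact level='Yes') alpha=0.05". It has no MISSING option, and no imputation step precedes it.

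**Derivation.** SAP 18.3 calls a zero sum of the two sign scores resolution and adds: "Any non 0 sum means not reaching clinical resolution". It then says: "If either individual score is missing, clinical resolution status will be set to missing".

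**Missing Day 6 status.** Protocol 9.8.2 (Amendment 3) carries the last post-baseline observation forward. The SAP works from Amendment 4.0, which was not supplied. In the SAP, LOCF appears only in the abbreviation list. SAP 17 drops hypothesis testing and most efficacy analyses and does not mention LOCF.

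**Table shells.** SAP 1 says: "Specifications for tables, figures, and listings are contained in a separate document".

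**The concern.** Clinical resolution at Day 6 is the primary endpoint and one of only three efficacy endpoints still summarised by arm. Three calculations fit the SAP text: observed cases, all subjects in the population, or LOCF. They can give different percentages. The SAP states a percentage base for disposition (section 5) and demographics (section 7), but not for this endpoint, and protocol 9.4 leaves the handling of missing data to the SAP.

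Read literally, the text and code give observed cases. Discontinued subjects are sent to Visit 5, and SAP 18.2 uses CRF visits, so someone who stops before Day 6 may have no Visit 3 status and would leave the denominator. An ITT table built that way describes only the graded subjects. If dropout relates to outcome or differs by arm, the descriptive rates shift.

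The second issue is one of logic. The scales run 0–4 and 0–3, so a single recorded score of 1 or more makes the sum non-zero whatever the other score is. Coding that subject as missing discards a known outcome.

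**Working it through.** **Plan figures first.** SAP 2.5 plans 140 SHP640 and 70 placebo subjects in mITT at 31% versus 11%, with 90% power by two-sided Fisher's exact test at 5%. Full enumeration gives 91.8%, in line with the plan. 350/(1 − 0.35) = 538.5, which the SAP rounds to about 540; split 2:2:1 this is 216, 216 and 108. These figures are not disputed.

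**Denominator, planned ITT sizes.** Inputs: 216 and 108 subjects; 31% and 11% as observed-case rates; 8% missing. The 8% is the earlier study's dropout figure (SAP 2.5), used here as an assumption.
- Missing: 0.08 × 216 = 17.3, taken as 17; 0.08 × 108 = 8.6, taken as 9. Observed: 199 and 99.
- Resolved: 0.31 × 199 ≈ 62; 0.11 × 99 ≈ 11.

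| Arm | Observed cases x/(N − m) | Exact 95% CI | All subjects x/N |
|---|---|---|---|
| SHP640 | 62/199 = 31.2% | 24.8% to 38.1% | 62/216 = 28.7% |
| Placebo | 11/99 = 11.1% | 5.7% to 19.0% | 11/108 = 10.2% |

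In general the all-subject rate is p(1 − m). For 6% to 8% missing, 31% becomes 0.31 × 0.94 = 29.1% to 0.31 × 0.92 = 28.5%, and 11% becomes 10.3% to 10.1%.

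**Denominator, planned mITT sizes, resolved counts held at 43/140 and 8/70.**
- All subjects: 30.7% and 11.4%, difference 19.3 points.
- Observed cases, 8% missing (11 and 6): 43/129 = 33.3% and 8/64 = 12.5%, difference 20.8 points.
- Unequal missingness (assumed 16% in SHP640, 8% in placebo): 43/118 = 36.4% and 12.5%, difference 23.9 points.

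**One-sign rule alone.** The documents give no frequency. If a fraction f are proven failures coded as missing, the rate reads p/(1 − f). For an assumed f of 0.5% to 5%, 31% reads 31.2% to 32.6%, and 11% reads 11.1% to 11.6%. In counts, 43/140 (30.7%, exact CI 23.2% to 39.1%) reads 43/138 (31.2%) with 2 dropped and 43/133 (32.3%) with 7 dropped.

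**Offset.** One-sign missingness also removes subjects whose recorded score is 0. Assume 2% proven failures and 2% with one score 0 and the other missing, 62% of the latter resolved. Then 0.62 × 2% = 1.24% resolved among the 4% affected, which is 31%: missingness unrelated to outcome.
- Resolved and fully graded: 0.31 − 0.0124 = 0.2976.
- Current rule: 0.2976/0.96 = 31.0%, the true rate.
- Recoding failures only: 0.2976/0.98 = 30.4%.
- All subjects, missing counted as not resolved: 29.8%, with or without the recode.

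So the recode by itself lowers the observed-case rate below the truth, because known failures return while possible successes stay out.

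**The case against.** **The SAP is not truly silent.** 18.3 sets status to missing, 10.2 imputes nothing, and the code is observed-case; SAP 17 limits the statistics to what 10.2 outlines, which contains no LOCF. Much of this stands: observed cases is the natural reading. It remains an inference from code labelled as an example. The table specifications, or the reporting conventions cited in SAP 18.1, may define n; neither was supplied.

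**The one-sign rule is uniform and nearly empty.** Both signs are scheduled at the same visits, and the same missing-component rule serves the other score-based endpoints. This stands as to size. A sum does need both parts; a resolved/not-resolved status sometimes does not.

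**Counting missing as failure is a preference.** It stands; no document prescribes it. It therefore belongs beside the observed-case figure, not in its place.

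**Stronger readings.** A reader might infer that the rule inflates the primary endpoint. The documents do not support that, since zero-and-missing subjects are dropped too and can cancel the effect. A reader might also infer that HSV-positive subjects are necessarily ungraded in ITT. Protocol 4.4 lists safety assessments for them without the two sign gradings, but does not forbid grading, and that text is Amendment 3. Nor can LOCF be called wrongly abandoned: its status under Amendment 4.0 is unknown.

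**Conclusion.** The point holds as a minor one. The SAP text does not state the denominator for its main efficacy proportions; followed literally, it yields observed-case rates even under an ITT label, and it leaves the status of LOCF unsaid. At an assumed 8% missing the denominator choice moves the rates by about 2.5 points in SHP640 and 0.9 points in placebo, well within the exact intervals. The one-sign rule is a genuine inconsistency, probably rare and small, and can move the observed-case rate either way.

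The sizes rest on planning rates and on an earlier study's mITT dropout applied to planned ITT numbers; this trial stopped early, so they are illustrative. A reader might infer that a conclusion about efficacy is at risk. It is not: SAP 2.6 and 10.2 rule out hypothesis testing, and the signs and resolution status are listed by subject for ITT (Listings 16.2.6.1 and 16.2.6.2), so either rate can be rebuilt. Only descriptive accuracy is affected.

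**What to change.** **SAP 10.2, Tables 14.2.1.1 and 14.2.1.4.** Keep the observed-case proportion and label it so. Beside it give the proportion of all mITT (or ITT) subjects with missing status counted as not resolved, and the number missing by arm and visit. State whether LOCF is dropped. If the table specifications already define n, make the SAP sentence match.

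**SAP 18.3.** Code clinical resolution as No when any recorded score is above 0. Code it as missing only when both scores are missing or the single recorded score is 0.

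Adopt the 18.3 recode only together with the all-subject row, for the reason shown in the offset example. The all-subject rate is unchanged by the recode; what it corrects is the count of missing.

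**Cost.** A one-line recode, a sentence or two in 10.2, and one extra row with missing counts per table; no new data. The downside is a slightly lower all-subject rate to explain, for example 28.5% beside 31% at 8% missing.

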18.4 Repeated or Unscheduled Assessments of Safety Parameters

Assessments obtained on the scheduled CRF visits will be included in summary tables. Additional repeated or unscheduled assessments will not be included in the by visit summary tables, but will be included in subject listings.

18.5 Missing Date of Investigational Product

When the date of the last dose of investigational product is missing for a subject in the Safety Population, all efforts should be made to obtain the date from the investigator. If it is still missing after all efforts, then the last visit date when investigational product was returned will be used in the calculation of treatment duration.

18.6 Missing Date Information for Prior or Concomitant Medications

For prior or concomitant medications, including rescue medications, incomplete (ie, partially missing) start date and/or stop date will be imputed. When the start date and the stop date are both incomplete for a subject, impute the start date first.

18.6.1 Incomplete Start Date

The following rules will be applied to impute the missing numerical fields. If the stop date is complete and the imputed start date is after the stop date, then the start date will be imputed using the stop date.

Missing day and month

- If the year of the incomplete start date is the same as the year of the date of the first dose of investigational product, then the day and month of the date of the first dose of investigational product will be assigned to the missing fields
- If the year of the incomplete start date is before the year of the date of the first dose of investigational product, then December 31 will be assigned to the missing fields
- If the year of the incomplete start date is after the year of the date of the first dose of investigational product, then 01 January will be assigned to the missing fields.

Missing month only

- The day will be treated as missing and both month and day will be replaced according to the above procedure.

Missing day only

- If the month and year of the incomplete start date are the same as the month and year of the date of the first dose of investigational product, then the day of the date of the first dose of investigational product will be assigned to the missing day
- If either the year is before the year of the date of the first dose of investigational product or if both years are the same but the month is before the month of the date of the first dose of investigational product, then the last day of the month will be assigned to the missing day
- If either the year is after the year of the date of the first dose of investigational product or if both years are the same but the month is after the month of the date of the first dose of investigational product, then the first day of the month will be assigned to the missing day.

18.6.2 Incomplete Stop Date

The following rules will be applied to impute the missing numerical fields. If the date of the last dose of investigational product is missing, then replace it with the last visit date. If the imputed stop date is before the start date (imputed or non-imputed start date), then the imputed stop date will be equal to the start date.

Missing day and month

- If the year of the incomplete stop date is the same as the year as of the date of the last dose of investigational product, then the day and month of the date of the last dose of investigational product will be assigned to the missing fields
- If the year of the incomplete stop date is before the year of the date of the last dose of investigational product, then 31 December will be assigned to the missing fields
- If the year of the incomplete stop date is after the year of the date of the last dose of investigational product, then 01 January will be assigned to the missing fields.

Missing month only

- The day will be treated as missing and both month and day will be replaced according to the above procedure.

Missing day only

- If the month and year of the incomplete stop date are the same as the month and year of the date of the last dose of investigational product, then the day of the date of the last dose of investigational product will be assigned to the missing day
- If either the year is before the year of the date of the last dose of investigational product or if both years are the same but the month is before the month of the date of the last dose of investigational product, then the last day of the month will be assigned to the missing day
- If either the year is after the year of the last dose of investigational product or if both years are the same but the month is after the month of the date of the last dose of investigational product, then the first day of the month will be assigned to the missing day.

18.7 Missing Date Information for Adverse Events

For AEs, incomplete (i.e. partially missing) start dates will be imputed if the subject is missing whether the event occurred prior to the first study drug dose. Incomplete stop dates will not be imputed.

18.7.1 Incomplete Start Date

If incomplete state date needs to be imputed, then follow same rules as in Section 18.6.1.

18.8 Missing Severity Assessment for Adverse Events

If severity is missing for an AE starting prior to the date of the first dose of investigational product, then a severity of “Mild” will be assigned. If the severity is missing for an AE starting after the first dose of investigational product, then a severity of “Severe” will be assigned. The imputed values for severity assessment will be used for incidence summaries. while both the actual and imputed values will be used in data listings.

18.9 Missing Relationship to Investigation Product for Adverse Events

If the relationship to investigational product is missing for an AE starting after the first dose of investigational product, a causality of “Related” will be assigned. The imputed values for relationship to double-masked investigational product will be used for incidence summaries, while both the actual and imputed values will be presented in data listings.

20. APPENDIX

20.1 Example SAS Code for Generating Descriptive Statistics

```
*For binary endpoint;  
proc freq data = testData;  
tables binary_endpoint / binomial (exact level='Yes') alpha=0.05;  
by visit treatment;  
run;
```

